Currently, there is limited data from patients with both a CardioMEMS device and LVAD. The purpose of this post market study is to characterize and evaluate hemodynamic-guided management in patients that have per indications received a HeartMate LVAD and a CardioMEMS HF System. Patients will be managed with the goal of achieving a PA diastolic pressure in a target range of 8 to 15 mmHg. This range is slightly higher than the PA diastolic pressure range found in healthy subjects (4 to 12 mmHg)⁸ and allows for volume and pressure changes during the course of the day and avoid hypovolemia. The learnings from this feasibility

This confidential document is the property of Abbott and shall not be reproduced, distributed, disclosed or used without the express written consent of Abbott.

study will be used to develop CardioMEMS-guided treatment strategies to improve clinical outcomes of HeartMate patients with poor functional status and provide meaningful evidence for designing future studies.

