8.2 SAFETY REPORTING

Safety surveillance within this study and the safety reporting performed both by the investigator and Sponsor for these market release devices starts after the indicated devices have been implanted and as soon as the subject is enrolled in this clinical investigation (refer to section 5.4 for enrollment timing). Procedure related adverse events, prior to both devices being successfully implanted, do not require reporting within this study.

The safety surveillance and the safety reporting will continue until the last investigational visit (six months) has been performed, the subject is deceased, the subject/investigator concludes his participation into the clinical investigation or the subject withdrawal from the clinical investigation.

For purposes of this study, any adverse event that is possibly or likely related to either device, will be collected throughout the clinical investigation. Refer to device specific user manuals. Additionally, adverse events that are possibly or likely related to treating to target ranges (detailed below) will be reported to the Sponsor on a CRF.

Adverse events will be monitored until they are adequately resolved or the subject has ended his/her participation in the trial, whichever comes first. The status of the subject's condition should be documented at each visit.

For the purposes of this clinical investigation, the following events that could be potentially caused by using the CardioMEMS™ device to manage PA pressures to target ranges in patients with HeartMate™ Left Assist devices require reporting. The following adverse events will be required to be reported within the study if they are possibly or likely related to the study procedures or to either of the study devices (see Appendix B for definitions):

- Cardiac Arrhythmias
 - Ventricular Arrhythmia
 - Supraventricular Arrhythmia
 - Both (Ventricular and Supraventricular Arrhythmia)
- Strokes regardless of their types and etiology
 - Hemorrhagic Stroke
 - Ischemic Stroke
 - Debilitating Stroke
- Other Neurological Events felt to be related to managing PA pressures
- Renal Dysfunction secondary to heart failure
- Respiratory Failure secondary to cardiovascular cause
- Right Heart Failure
- Syncope/presyncope/dizziness and hypovolemia
- Worsening Heart Failure
- Other Adverse Event that in the opinion of the investigator are suspected to be related to using the CardioMEMS device to manage PA pressures to target ranges.

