This confidential document is the property of Abbott and shall not be reproduced, distributed, disclosed or used without the express written consent of Abbott.

Abnormal kidney function requiring dialysis (including hemofiltration) in Subjects who did not require this procedure prior to implant, or a rise in serum creatinine of greater than 3 times baseline or greater than 5 mg/dl sustained for over 48 hours.

Chronic Renal Dysfunction

An increase in serum creatinine of 2 mg/dl or greater above baseline, or requirement for hemodialysis sustained for at least 90 days.

Right Heart Failure

Symptoms and signs of persistent right ventricular dysfunction requiring RVAD implantation, or requiring inhaled nitric oxide or inotropic therapy for a duration of more than 1 week at any time after LVAD implantation.

Syncope/Presyncope/dizziness or hypovolemia

Transient sensation that may lead to inability to maintain an upright posture. Can be felt as lightheadedness, muscular weakness, blurred vision, feeling faint and. In extreme cases could lead to fainting (syncope).

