Appendix F: Management of Hemodynamic Parameters

The CardioMEMS HF System allows intermittent assessment of pulmonary artery systolic, diastolic and mean pulmonary artery pressures. Hemodynamic information obtained by the system should be used for clinical decision making in addition to symptoms, weights or physical examination (traditional markers of volume).

Target Pulmonary Artery Diastolic Pressure Range: 8 - 15 mmHg

Initially, thresholds will be set automatically at the CardioMEMS commercially acceptable range. The physician will then adjust the thresholds to the specified range above, specifically for each patient. These threshold notifications are intended to guide the physician to review the Merlin.net website. Every attempt should be made to keep the pulmonary artery pressures within the specified pulmonary artery pressure ranges utilizing the guidelines. In order to clinically manage patient's PA pressures, the physician must review the PA pressure measurements on a frequent basis, for example, some patients may require a daily review of their PA pressure measurements, while some patients may need a weekly review. The physician or designee has unlimited access to the Merlin.net website.

An elevation of pressures beyond the patient's pressure ranges should be considered a volume overloaded status and should be managed using one of the recommended treatment options listed below.

A decrease in the pulmonary pressures below the patient's pressure ranges should be considered a volume depletion event and managed using one of the recommended treatment options listed below.

Diuretics and vasodilators should be adjusted based on the patient's baseline diuretic requirement, knowledge of the patient's prior response to these agents, and clinician judgment to accomplish the pressure goals set forth in this guideline.

The PA pressure readings should be used in addition to weights, signs and symptoms, laboratory values and other traditional markers of volume in the management of heart failure. It is important to review the trend of PA pressures. As with all other diagnostic information, physicians should consider the entire medical history of each patient when initiating or modifying therapies.

Recommended Treatment Options:

- Diuretic Management
- Vasodilators such as nitrates and hydralazine
- Titration of HF medications
- LVAD Speed Changes

Table 6 – Recommended Frequency of CardioMEMS HF System Review

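### Hypovolemia shares one reportable category, and one symptom-only definition, with syncope and dizziness, so the planned adverse event data cannot separate it

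*Combined protocol and SAP*

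**What the plan says.** Section 2 sets the PA diastolic target at 8 to 15 mmHg, a little above the 4 to 12 mmHg it gives for healthy people. One reason offered is that the range "allows for volume and pressure changes during the course of the day and avoid hypovolemia".

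Section 8.2 lists "Syncope/presyncope/dizziness and hypovolemia" as a single reportable item. Listed events are reported "if they are possibly or likely related to the study procedures or to either of the study devices", and sites are sent to Appendix B for definitions. The list closes with an item for other adverse events that the investigator suspects are related to managing PA pressure to target.

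Appendix B titles the entry "Syncope/Presyncope/dizziness or hypovolemia" and gives one definition for all of it: "Transient sensation that may lead to inability to maintain an upright posture". It adds examples of how this may feel and notes that it may end in fainting. No volume, pressure, laboratory or pump criterion appears.

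Appendix F, which is management guidance, says: "A decrease in the pulmonary pressures below the patient's pressure ranges should be considered a volume depletion event". It also says: "The PA pressure readings should be used in addition to weights, signs and symptoms, laboratory values and other traditional markers of volume", and asks for the trend to be reviewed. Table 6 labels low PA pressure as hypovolemic.

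On analysis, Section 6.1.3 summarizes adverse events at 1, 3 and 6 months in four types formed by seriousness and device-relatedness. Section 6.1.1, item 3, reports the percentage of measured days on which PA diastolic pressure is between 8 and 15 mmHg.

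**The concern.** Hypovolemia is a central harm for this design. Section 2 cites avoiding it when justifying the range, Section 4.1 recommends diuretic adjustment as the first approach, and Section 8.2 presents the listed events as ones that managing to target could cause. Evaluating target ranges is an objective in Section 4.2, and the results are meant to shape later studies.

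A designer of the next study will want to know how often patients managed to this range became volume depleted. The category that should answer this is defined by a symptom that has many causes, and it leaves out volume depletion without the symptom. Elsewhere Appendix B does give objective criteria, for example creatinine thresholds for renal dysfunction and imaging for stroke, so the lack of one here is not the document's general style.

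**Working it through.** The plan states no expected rate, precision or power for this event, and the sample size of 100 comes without a calculation, so there is no figure to reproduce. The check is a comparison of the texts, followed by two illustrations.

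**Step 1. Apply the wording of Section 8.2 and Appendix B to the possible cases.**

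| Case | Meets the Appendix B wording? | Place on the Section 8.2 list |
|---|---|---|
| Documented hypovolemia with lightheadedness, judged possibly related | Yes | Combined item |
| Documented hypovolemia, no sensation | No | Closing item only, if the investigator suspects a link to managing to target |
| Dizziness of another mechanism, judged possibly related | Yes | Combined item |
| Dizziness judged unrelated | Yes, but fails the relatedness condition | Not reported |
| Low reading alone | No | None; handled as management under Appendix F |

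Rows 1 and 3 fall together, and rows 1 and 2 fall apart. The category is therefore neither specific to hypovolemia nor complete for it.

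**Step 2. Ask whether the planned summaries recover the split.** The four types in Section 6.1.3 do not mention event term, so even the combined item has no stated row. Endpoint 3 gives an in-range percentage p, and the remaining 100 − p is not divided. If p were 60%, days below 8 mmHg could be anywhere from 0% to 100 − 60 = 40% of measured days.

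**Step 3. Size in the adverse event data.** Suppose c of n = 100 subjects have the combined event. The number of these with hypovolemia, x, is bounded only by 0 ≤ x ≤ c. Exact (Clopper-Pearson) 95% limits for x of n are the 2.5% point of Beta(x, n − x + 1) and the 97.5% point of Beta(x + 1, n − x). For x = 0 the lower limit is 0 and the upper is 1 − 0.025^(1/100) = 3.6%. All counts below are assumed.

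| Combined event, c of 100 | 95% interval for c | Hypovolemia share none | Share half | Share all |
|---|---|---|---|---|
| 10 | 4.9% to 17.6% | 0% (0 to 3.6%) | 5% (1.6 to 11.3%) | 10% (4.9 to 17.6%) |
| 20 | 12.7% to 29.2% | 0% (0 to 3.6%) | 10% (4.9 to 17.6%) | 20% (12.7 to 29.2%) |

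Symptom-free cases from row 2 of Step 1 lie outside c, so c is not an upper bound on all hypovolemia. With its own category, 5 of 100 would be reported with an interval of 1.6% to 11.3%, which is usable for planning.

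**The case against.** The strongest case against has four parts.

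*There is only one adverse event definition.* A reader might infer that Section 8.2, Appendix B and Appendix F give three competing definitions, and that every reading below range counts as an event under Appendix F. The documents do not support that. Section 8.2 defers to Appendix B, which makes the change from *and* to *or* between them minor. Appendix F tells clinicians how to respond to pressures and says nothing about adverse event reporting. It also requires trend, symptoms, laboratory values and other markers to be weighed. This part of the objection stands in full. What remains is that a similar term carries a pressure-based meaning in Appendix F and Table 6 and a symptom meaning in Appendix B, which is worth reconciling.

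*The capture gap is partly closed.* The closing item in Section 8.2 can take symptom-free hypovolemia, and the relatedness condition removes dizziness judged unrelated. Both stand, and they narrow the gap. They do not close it: similar events would sit under two headings, and possibly related dizziness of any mechanism stays in the combined one.

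*The data are already collected.* Pressures are transmitted throughout. Sections 4.1, 5.6 and 5.8.1 require drug and pump speed changes to be logged with reasons, and Sections 4.1 and 5.6 require out-of-range episodes to be explained. This stands, and it makes the fix cheap. It does not supply the missing summary.

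*The study is a descriptive feasibility study, and hypovolemia is not one of its ten endpoints.* True, and it limits the weight of the point. A descriptive safety table still has to describe the harm it lists.

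**Conclusion.** The point holds in a limited form. As written, the combined category misclassifies hypovolemia in both directions, and neither the adverse event summary nor endpoint 3 restores the distinction. With 10 combined events in 100 subjects, between 0 and 10 could involve hypovolemia; with 20, between 0 and 20. These counts are assumed and take all 100 subjects as enrolled and contributing.

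A reader might go further and infer that the frequency of volume depletion cannot be estimated at all. That is too strong. The combined rate can be estimated if tabulated, and days below 8 mmHg can be counted from the stored pressures, although no such summary is planned. What cannot be obtained from the planned adverse event data is clinical hypovolemia as distinct from dizziness and syncope. No figure is offered for how often readings would fall below 8 mmHg, because the documents give neither the mean nor the day-to-day spread, and a low reading is not in itself a reportable event.

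The case report forms are not in the documents, so a separate hypovolemia field may exist. If it does, the definition and the tables would still need the change. This should be corrected, but it does not threaten the study as a whole.

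**What to change.** 1. In Section 8.2 and Appendix B, split the entry into (a) syncope, presyncope or dizziness and (b) hypovolemia. Give (b) its own clinician-documented definition, stating whether a low pressure reading alone qualifies. The clinical criteria are for the sponsor and the Steering Committee to set.
2. Reconcile the use of volume depletion and hypovolemic in Appendix F and Table 6 with that definition, for example by a sentence saying that those terms are management labels and do not define a reportable event, if that is the intent.
3. In Section 6.1.3, tabulate by event term, with (a) and (b) on separate rows.
4. In Section 6.1.1, item 3, add the percentages of measured days below 8 mmHg and above 15 mmHg, reported separately alongside the in-range figure. Use the pressures and the medication and speed logs already collected.

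The cost is definition wording, one more adverse event category and a few table rows. The pressure summary needs no new data collection.

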Appendix C: NYHA Classification

NYHA Classification must be performed by an advanced practice physician, or by an experienced clinician designated by the principal investigator in writing.

Table 4 – NYHA Classification

Classification	Definition
I	Cardiac disease without resulting limitations of physical activity. Ordinary physical activity does not cause undue fatigue, palpitations, dyspnea or chest pain.
II	Cardiac disease resulting in slight limitation of physical activity. Subjects are comfortable at rest. Ordinary physical activity results in fatigue, palpitation, dyspnea, or chest pain.
IIIA	Cardiac disease resulting in marked limitations of physical activity. Subjects are comfortable at rest. Less than ordinary physical activity causes fatigue, palpitation, dyspnea, or chest pain.
IIIB	Cardiac disease resulting in marked limitations of physical activity. Subjects are comfortable at rest. Mild physical activity causes fatigue, palpitation, dyspnea, or chest pain.
IV*	Cardiac disease resulting in inability to carry on any physical activity without discomfort. Symptoms of cardiac insufficiency or of the chest syndrome may be present even at rest. If any physical activity is undertaken, discomfort is increased.

*For all post-enrollment NYHA assessments, any patient who is inotrope dependent will be considered NYHA Class IV.

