4.4.1 Inclusion Criteria

To participate in this clinical investigation, the subject must meet all of the following inclusion criteria:

1. Subject has CardioMEMS HF PA Sensor and a commercially-approved HeartMate LVAD (Group A)

OR

This confidential document is the property of Abbott and shall not be reproduced, distributed, disclosed or used without the express written consent of Abbott.

Subject has commercially-approved HeartMate LVAD is experiencing NYHA class III symptoms, and has had a previous HF hospitalization and meets FDA indications for CardioMEMS. The CardioMEMS sensor must be implanted within 72 hours of consent (Group B)

2. Signed an informed consent form and agreed to provide access to patient and device data (including CardioMEMS Merlin.net data)
3. No connectivity or transmission problems with CardioMEMS
4. On HeartMate LVAD support for at least 3 months
5. Age \geq 18 years

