5.4 POINT OF ENROLLMENT

For Group A, the subject is considered enrolled (and will count toward the analysis,) when the subject has provided written Informed Consent, has been confirmed to meet all inclusion criteria and none of the exclusion criteria. For Group B, the subject is considered enrolled (and will count toward the analysis,) when the subject has provided written Informed Consent, has been confirmed to meet all inclusion criteria and none of the exclusion criteria and has been successfully implanted with CardioMEMS. Patients who do not have a successful CardioMEMS implant after consent, will not be considered enrolled.

The Principal Investigator or delegated study personnel will record enrollment information (name of the clinical investigation, date of consent and Inclusion/exclusion information) in the patient records and complete and submit applicable case report forms (CRF) in a timely manner, but not greater than 10 days from the study visit.

Notification of enrollment to the Sponsor is considered to have occurred when the Sponsor has received the applicable CRF. For Group B, the component information CRF will be completed upon successful implant and submitted to the sponsor.

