5.5.1 Baseline

The following baseline assessments and information will be collected after informed consent is obtained at the baseline visit. For Group A patients, these assessments will be done after consent. For Group B patients, assessments will be performed after consent and within 3 days prior to the CardioMEMS™ HF System implant.

- Medical history, physical and documentation of Inclusion/ exclusion information,
- Heart failure visit assessment including assessing and recording NYHA class, height, weight and vital signs
- Documentation of demographic information
- Documentation of HeartMate device model and CardioMEMS™ study device sensor serial number information (for group B this CRF will be completed after successful CardioMEMS implant)
- Current Medications: anticoagulation/anti platelet, and cardiovascular medications including ACE inhibitors, ARBs, beta blockers, nitrates, hydralazine, aldosterone antagonists, digoxin and diuretics. Other medications do not need to be tracked.
- Documentation of current pump parameters
- Administer Six Minute Hall Walk test (6MHWT). For Group A, CardioMEMS PA reading taken before 6MHW test (at rest) and immediately following 6MHW test (see Appendix D), ideally within one minute of test
- Administer EQ-5D-5L survey

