6.1 ANALYSIS OF ENDPOINTS

6.1.1 Descriptive Endpoints

The following endpoints will be analyzed using descriptive statistics. Continuous variables will be summarized using numbers of subjects, mean, standard deviation, median, minimum, and maximum. Categorical variables will be summarized using frequency and percentages. Rate data will be summarized using events per patient-time.

1. Change in Six Minute Hall Walk (6MHW) distance will be summarized as change from baseline and using raw values, at 1, 3, and 6 months.
2. Changes in CardioMEMS™ PA pressure over time will include PA systolic, diastolic and mean pressures; heart rate; and cardiac output (calculated using latest algorithm for CardioMEMS) and will be summarized at baseline, throughout the study, and at 6 months.
3. Percentage of days over 6 months that PA diastolic pressure is between 8 and 15 mmHg will be summarized using the total number of days that pressures were measured as the denominator. The percentage will also be calculated at different points during the study. This endpoint will be used to assess the impact of medication and pump speed changes on PA pressures.
4. Changes in PA pressure before the 6MHW test to after the 6MHW test will be summarized at baseline (Group A only) and at 1, 3, and 6 months for both groups.
5. Device malfunction will include all instances of loss of performance of either device and will be summarized separately by device and type of loss of performance at 1, 3, and 6 months.
6. NYHA classification will be analyzed as a categorical variable and as a continuous variable at baseline, 1, 3, and 6 months. Change from baseline in NYHA will be analyzed similarly.
7. Health related quality of life (EQ-5D-5L) total score and visual analogue scale will be scored using the recommended scoring algorithms and analyzed at baseline, 1, 3, and 6 months. The change from baseline in EQ5D-5L will be analyzed similarly.
8. All-cause hospitalization rate will be summarized over 6 months in units of events per patient-time.
9. Heart failure hospitalization rate including emergency department visits, or unscheduled clinic visits for worsening HF, volume management, and/or cardiovascular medication management will be summarized over 6 months in units of events per patient-time.
10. Change in 6MHWD, NYHA class, EQ-5D-5L, or unscheduled hospitalizations will be analyzed descriptively according to subgroups based on PA diastolic pressure.

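### The rule setting inotrope-dependent patients to NYHA class IV applies only after enrollment, so some clinically unchanged patients would be scored as worse than baseline

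*Combined protocol and SAP*

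**What the plan says.** The footnote to Table 4 in Appendix C reads: "For all post-enrollment NYHA assessments, any patient who is inotrope dependent will be considered NYHA Class IV". The baseline visit (Section 5.5.1) asks only for "Heart failure visit assessment including assessing and recording NYHA class, height, weight and vital signs" and says nothing about inotropes in assigning the class. Table 2 likewise lists NYHA class at every visit without a scoring rule.

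Section 6.1.1 then puts the two ends together. Item 6 says "NYHA classification will be analyzed as a categorical variable and as a continuous variable at baseline, 1, 3, and 6 months", followed by "Change from baseline in NYHA will be analyzed similarly". Item 10 uses it again: "Change in 6MHWD, NYHA class, EQ-5D-5L, or unscheduled hospitalizations will be analyzed descriptively according to subgroups based on PA diastolic pressure".

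On who enters and when, a Group B patient "is experiencing NYHA class III symptoms, and has had a previous HF hospitalization" (Section 4.4.1). Section 5.5.1 places the Group B baseline before the sensor: "For Group B patients, assessments will be performed after consent and within 3 days prior to the CardioMEMS™ HF System implant". Section 5.4 places Group B enrollment after it: "Patients who do not have a successful CardioMEMS implant after consent, will not be considered enrolled". The exclusion criteria in Section 4.4.2 do not mention inotropes.

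**The concern.** A change score is interpretable only if both ends are measured in the same way. Here the baseline end is the clinician's rating, and the follow-up end is overridden to IV for one kind of patient. If that patient was already on inotropes at baseline and was rated below IV, the override creates a worsening that did not happen.

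The patients in question can enter, because inotrope dependence is not an exclusion. They may also be hard to identify afterwards. The medication classes named in Section 5.5.1 include digoxin but not intravenous inotropes, and medications outside the listed groups need not be tracked.

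What is at stake is modest. Section 6 intends the results, including any p-values, to help choose endpoints for future trials. An artificial shift toward worsening would make NYHA change look slightly less responsive than it is.

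**Working it through.** The plan gives no figure that depends on this rule. The sample size of 100 (Section 6.2) comes with no alpha, power or effect size, so there is nothing to reproduce. The check is a direct scoring exercise.

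**Is baseline before enrollment?**
- Group B: yes. Assessments come before the implant (Section 5.5.1), and the patient is enrolled only after a successful implant (Section 5.4). The rule cannot apply at baseline.
- Group A: unclear. Enrollment is consent plus confirmed eligibility (Section 5.4), baseline follows consent (Section 5.5.1), and Table 2 puts enrollment and baseline in one column. Section 5.5.2, however, describes the Month 1, 3 and 6 visits as the ones that follow enrollment, which favors reading baseline as outside the rule.

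**Score for a patient who is dependent throughout and clinically unchanged.** With four-level coding (I = 1 to IV = 4), change = follow-up score − baseline score.

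| Clinician class at both times | Rule at follow-up only (current) | Rule at all visits | Clinician rating at all visits |
|---|---|---|---|
| I | 4 − 1 = +3 | 4 − 4 = 0 | 0 |
| II | 4 − 2 = +2 | 0 | 0 |
| III | 4 − 3 = +1 | 0 | 0 |
| IV | 4 − 4 = 0 | 0 | 0 |

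A Group B patient enters with class III symptoms, so the relevant row is +1. The rows for I and II could matter only in Group A.

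**Effect on the summary.** Shift in mean change = (number affected × class shift) / N. The share affected is not in the documents. The values below are assumptions, with N = 100 (the maximum enrollment) and all affected patients rated III.

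| Assumed share affected | Shift in mean change | Added to share worsened | Chance of at least one such patient, 1 − (1 − p)^100 |
|---|---|---|---|
| 1% | 1 × 1/100 = +0.01 | 1 point | 63% |
| 2% | 2 × 1/100 = +0.02 | 2 points | 87% |
| 5% | 5 × 1/100 = +0.05 | 5 points | 99% |
| 10% | 10 × 1/100 = +0.10 | 10 points | nearly 100% |

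In a smaller group each case weighs more. If Group B had 50 or 25 patients (assumed sizes), one affected patient would shift its mean change by 1/50 = +0.02 or 1/25 = +0.04.

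**Coding.** Table 4 splits class III into IIIA and IIIB, but no numeric coding is given for the continuous analysis. If the two were coded as separate steps, a move from IIIA to IV would count as two steps instead of one.

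**The case against.** The strongest reply has four parts.

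*Group A may not be affected.* If its baseline counts as post-enrollment, the rule applies at both ends and the artefact is confined to Group B. This stands as an open question. It does not remove the problem, because Groups A and B would then have baselines scored by different rules, and Section 6 analyzes them together as well as separately.

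*The number may be very small.* This stands. The documents give no prevalence. Appendix B mentions inotropes only in defining right heart failure, a reportable adverse event. That suggests, without proving it, that inotrope need is seen as a complication and not as a usual state at entry.

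*Applying the rule at baseline creates the opposite artefact.* A patient with class III symptoms on inotropes at baseline and class III symptoms off them later would be scored IV to III, an improvement. In a single-arm study, that errs toward apparent benefit. The objection is correct, and it is the reason to report the clinician-rated version alongside.

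*Status could be recovered later.* Medical history and cardiovascular medications are collected, and Section 11.2 gives access to source data. This is partly right. Recovery is possible but not assured by the listed data fields.

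A reader might also infer more than the documents support:
- **That every inotrope-dependent Group B patient has a worsening built in.** The artefact needs dependence at baseline, dependence at follow-up and a baseline rating below IV. A patient who starts inotropes after enrollment has truly changed.
- **That affected patients are the most likely to be outside the PA pressure range, so the endpoint 10 comparison is skewed between subgroups.** Nothing in the documents says so. Endpoint 10 is affected only because it uses the same change score.
- **That a patient weaned from inotropes who stays in class III has an improvement hidden.** Table 4 defines class by symptoms, and those are unchanged, so zero change is a fair clinician rating.

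**Conclusion.** The point holds in a limited form. The plan scores the two ends of NYHA change by different rules, and a clinically unchanged patient who is dependent at both times and rated below IV at baseline is counted as worsened. This is definite for Group B and the likelier reading for Group A. The direction is always toward worsening.

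The size is +1 class per affected patient rated III, or about +0.01 class in the mean and 1 percentage point in the share worsened for each 1% of patients affected. This rests on four-level coding and an assumed prevalence, and the true number may be small or zero.

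Severity is low. The endpoints are descriptive (Section 6), there is no success criterion (Section 6.4), and NYHA is one of ten endpoints. Nothing shows that a shift of this size would change a conclusion.

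**What to change.** In Appendix C and items 6 and 10 of Section 6.1.1:
- For the change analyses, score NYHA by the same rule at baseline and at follow-up.
- At baseline and at Months 1, 3 and 6, record both the clinician-rated class and inotrope dependence (yes/no), so that the rule does not overwrite the rating.
- Report NYHA change in two versions: the class IV rule applied at all visits, and the clinician-rated class at all visits.
- State that baseline is included in both groups, which settles what post-enrollment means for Group A. Give the numeric coding of IIIA and IIIB.
- Leave the class used for eligibility unchanged.

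The cost is one extra CRF field, a few sentences, and two NYHA values for a few patients. The rule-based version will score a weaned patient as improved, so neither version should be shown alone.
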